#### Secondary analysis

Secondary comparison of medical and surgical arms (preference and randomised subgroups combined):

- a. Comparison of proportions of women finding the procedure acceptable and rating the quality of care as 'excellent' the comparison will adjust for key baseline variables using logistic regression. We will also investigate the interaction between past history of TOP and intervention group on acceptability, and gestational age (as a continuous variable) and intervention group on acceptability.
- b. Comparison of mean values of psychological and rating scales the comparison will adjust for key baseline variables using multiple regression.
- c. Comparison of proportions of women with emergency admission and particular symptoms the comparison will adjust for key baseline variables using logistic regression.
- d. Comparison of WTP between those women in the combined groups.

Tertiary comparison of combined preference and randomised groups:

The aim of this comparison is to determine if receiving a preferred intervention improves key outcomes. Comparisons will be of acceptability, psychological and rating scales with methods as for secondary comparisons.

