# 14 STUDY DATA

# 14.1 Data collection

Baseline demographic data, including medical history and method of any previous termination, education level, occupation and income will be collected by the nurse practitioner or research nurse for all participants. Contact details (including where possible mobile phone numbers) and availability will also be collected.

Those expressing a procedure preference at baseline will be asked to nominate one or more reasons from a list of eight, developed as part of the pilot trial:

- 1. General anaesthetic (GA) want to be asleep (PS)
- 2. Fear of GA or desire to be awake and in control (PM)
- 3. Fetus do not want to see fetus (PS)
- 4. Pain perceived medical as more painful (PS)
- 5. Visits to hospital wanted minimum (PS)
- 6. Duration of procedure less time in hospital (PS)
- 7. Previous experience (i.e. had prior TOP) PM or PS
- 8. Other (<5% of responses)

All participants will be invited to return for an out-patient (hospital or community clinic) assessment 2 weeks after the procedure. Outcome data will be collected at 2 weeks (by interview and questionnaire) and at 3 months (by questionnaire) after the procedure. For women who do not attend their visit for 2 week follow up, collection of outcome data will be attempted where previously agreed via telephone interview, mobile text message & postal or web-based questionnaire. All visits and telephone interviews will be conducted by a research nurse.

Acceptability - This will be determined at 2 weeks and 3 months after the procedure by responses to the closed question 'If you ever have another termination of pregnancy, would you opt for the same method?'. This simple question has been used in previous preference

trials of TOP [14, 15] and can, if necessary, be easily determined by phone, questionnaire or text message.

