Strength of preference - To measure women's strength of preference for medical or surgical termination we will measure willingness to pay. This technique is being increasingly used in health technology assessment [32] and has been used previously for assessing strength of preference for abortion method [23, 33]. Interviews will be conducted, using the payment card method [34], in all women in the preference arm prior to the procedure where they will be asked to state their maximum 'willingness to pay' amount for the termination method they have chosen. Interviews will also be conducted on all women in both the randomised and preference arms at 2 weeks after the procedure when they will be asked to state their maximum 'willingness to pay' amount to receive their preferred option at a future date. The validity of women's responses will be tested by examining the correlation between stated 'willingness to pay' and level of income.

Satisfaction with care - The methodological pitfalls of measuring satisfaction with care have been reviewed recently [35]. Women will be asked to rate the quality of care during the termination and the counselling and support afterwards using a 5 point Likert scale (from excellent to poor) at 2 weeks and 3 months after the procedure. Measures in which patients are asked to rate the quality of aspects of their care show greater response variability than measures which seek direct ratings of satisfaction [36] and are better predictors of whether patients will return to the same doctor in the future [36]. For analysis we will distinguish those who rate their care as excellent from the remainder as this provides better discrimination [37]. A similar assessment has been used in our pilot trial. Ratings of care will be supplemented by information on satisfaction with care from the qualitative study.

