### Primary analysis

Main comparison of randomised arms:

- a. Comparison of proportions of women finding the procedure acceptable. We will also investigate the interaction between past history of TOP and intervention group on acceptability and gestational age (as a continuous variable) and intervention group on acceptability
- b. Comparison of mean values on psychological and rating scales.
- c. Comparison of proportions of women rating care as 'excellent'
- d. Comparison of WTP between those women in the two randomised groups.

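### The pooled willingness-to-pay comparison is the only partly self-selected comparison with no stated baseline adjustment, although the protocol expects willingness to pay to follow income

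*Protocol*

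**What the plan says.** Section 15.1, under Secondary analysis, compares the medical and surgical arms with the randomised and preference subgroups combined. It lists four items.

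- Item a covers acceptability and quality of care: "rating the quality of care as 'excellent' the comparison will adjust for key baseline variables using logistic regression".
- Item b covers the scales: "Comparison of mean values of psychological and rating scales the comparison will adjust for key baseline variables using multiple regression".
- Item c, on emergency admission and symptoms, also states adjustment by logistic regression.
- Item d reads "Comparison of WTP between those women in the combined groups". It names neither an adjustment nor a method.

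The tertiary comparison (preference versus randomised women) takes over the secondary methods, but WTP is not among its outcomes.

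The list under Primary analysis, restricted to the randomised arms, has its own WTP item: "Comparison of WTP between those women in the two randomised groups". None of the four items in that list states an adjustment.

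On income, section 14.1 says that "education level, occupation and income will be collected by the nurse practitioner or research nurse for all participants". Appendix B lists income again among the data to be collected with the WTP instrument. Section 14.1 also says: "The validity of women's responses will be tested by examining the correlation between stated 'willingness to pay' and level of income".

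**The concern.** A pooled medical-versus-surgical difference can be confounded when a baseline variable is related both to the outcome and to the method received. For WTP the protocol supplies the first link itself, since it treats a correlation with income as the sign that the answers are valid. The second link is possible because section 15.2 assumes that 50% of participants have a preference and so choose their method.

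The protocol recognises this risk for three of the four pooled comparisons and is silent on the outcome most directly tied to income. For any given income gap, the better the WTP answers pass the protocol's own validity test, the larger the distortion becomes. Strength of preference is a stated secondary objective (section 8), so the result will be read.

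**Working it through.** **Text comparison.** Under the secondary and tertiary headings, every comparison except item d either states baseline adjustment or inherits it. Under the primary heading no item does, so WTP is not singled out there.

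**The plan's own figures.** The protocol gives no figure for WTP. Its sample size does reproduce (two-sided 5% assumed, pooled variance, no continuity correction):

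- [1.96 × √(2 × 0.80 × 0.20) + 1.2816 × √(0.75 × 0.25 + 0.85 × 0.15)]² / 0.10² = 334.2, so 335 per arm and 670 in all.
- 670 / 0.6 = 1116.7 (stated 1116).
- 1116 / 0.5 = 2232.

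**Inputs for the illustration**

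- Responders: 0.6 × 2232 ≈ 1339. The 40% loss is stated for randomised women and is applied here to all, which is an assumption. The outcome is taken to be the two-week WTP, the one measured in every group.
- Half randomised, half by preference (section 15.2).
- Preference women split evenly between medical (PM) and surgical (PS), with 30/70 as a variant. Assumption.
- Income gap *d* between PM and PS women, in SD units: 0 to 0.5. Assumption.
- Income–WTP correlation *r*: 0.2 to 0.5. Assumption.
- Randomised arms balanced on income, with mean income equal to that of the preference women as a whole. No true WTP difference.

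**Formulas (even split)**

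- Half of each pooled arm is randomised and balanced, so the pooled income gap is 0.5 × *d*.
- Bias in WTP, in SD units = *r* × 0.5 × *d*.
- SE = √(1/669.5 + 1/669.5) = 0.0547.
- False-positive rate = Φ(bias/SE − 1.96) + Φ(−bias/SE − 1.96).

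Example: *d* = 0.3 and *r* = 0.3 give a bias of 0.045, a ratio of 0.045/0.0547 = 0.82 and a rate of about 13%.

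| PM–PS income gap (SD) | r = 0.2 | r = 0.3 | r = 0.5 |
|---|---|---|---|
| 0 | 5% | 5% | 5% |
| 0.1 | 5.4% | 5.9% | 7.4% |
| 0.2 | 6.5% | 8.5% | 15% |
| 0.3 | 8.5% | 13% | 28% |
| 0.5 | 15% | 28% | 63% |

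With a 30/70 split the rates are somewhat lower: 6.1%, 7.6% and 12% at a gap of 0.2; 7.6%, 11% and 22% at 0.3; 12%, 22% and 50% at 0.5.

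**The case against.** The best case for the protocol has five parts.

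1. **Item d is silent; it does not say unadjusted.** The choice of model and covariates for a secondary economic measure is often left to a statistical analysis plan. This is true in general. Here, however, the protocol settles adjustment item by item, so stating it for three items and not the fourth reads as a difference in method. A reader might infer a decision to leave WTP unadjusted. The text does not support that, and a drafting omission is just as likely.

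2. **No income imbalance is shown.** This stands. None of the specific preference reasons listed in section 14.1 is income. Section 7 says that choice of method is shaped more by social than by clinical factors, which makes an imbalance plausible but does not name income. The four-group baseline comparison in section 15.1 could reveal one, but it is not tied to the WTP analysis.

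3. **The randomised WTP comparison is protected.** This also stands. A reader might infer that WTP is singled out throughout section 15.1, or that the randomised comparison is confounded too. Neither holds: no primary item states adjustment, and randomisation balances income in expectation, leaving only differential loss to follow-up. Adjusting there would be an option for precision. The protocol states no power for WTP from which to measure a gain.

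4. **Larger error rates are easy to produce.** Applying a 0.2 SD gap directly to the pooled arms gives 11%, 20% and 45% at correlations of 0.2, 0.3 and 0.5. With an even split that needs about 0.4 SD between PM and PS women (0.2 / 0.5), because the randomised half dilutes the gap. The documents give no ground for so large a gap.

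5. **Items a to c are not shown to adjust for income either,** because key baseline variables are nowhere defined. This is correct, and it bears on how the fix is worded.

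**Conclusion.** The point holds for item d of the secondary analysis and no further. It is an inconsistency within the protocol's own list: followed as written, the pooled WTP comparison would be the one partly self-selected comparison made without adjustment, for an outcome the protocol expects to vary with a variable it already collects.

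The resulting bias is possible but not demonstrated. Under the even split its effect on a nominal 5% test runs from none (no income gap), through about 6.5% to 15% (gap 0.2 SD) and about 8.5% to 28% (gap 0.3 SD), to 63% at the far corner of the assumed range. All of this depends on an income gap and a correlation that the documents do not give, and on the follow-up assumption above. No stated figure in the protocol changes.

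**What to change.** Reword secondary item d along these lines: *Comparison of WTP between the combined medical and surgical groups, adjusting for key baseline variables including income by regression, with a model suited to skewed payment-card values with zeros.* Income has to be named, since repeating the clause from items a to c would not guarantee its inclusion. The payment card in Appendix B runs from £0 to an open category above £1000, hence the remark about the model.

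The cost is one sentence; the data are already planned. Women who decline to give their income will need missing-data handling, for example multiple imputation. A simple missing-income category would leave confounding by income within that category. Some residual confounding may remain in any case: adjustment restores the 5% rate in the illustration only if income is the sole confounder and is modelled correctly. Income adjustment in the randomised WTP comparison can be added for precision but is not required.

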Service users' evaluations of the care they have received are clearly important in the context of current initiatives to develop a more patient-centred NHS. Patient satisfaction with their care is the most commonly used indicator in research on patient evaluations [19], but definitions of satisfaction vary, and different measures incorporate different dimensions of the construct, such as adequacy, suitability and acceptability. A common problem with satisfaction measures is that they exhibit ceiling effects i.e. most patients report being satisfied, and distinctions between care of different quality are often not observed. This is likely to be a particular problem in areas such as termination of pregnancy, where patients are widely observed to experience a sense of relief after the procedure. Most studies of women's views about termination of pregnancy have reported procedure acceptability; typically women have been asked whether they would opt for the same method in the future or recommend the method to a friend [13, 17, 20]; data from randomised trials indicate that acceptability of both methods before 9 weeks gestation is high (63-92%) with 2-36% of women randomised to surgical termination of pregnancy preferring a medical procedure in future and 22-37% of women randomised to medical termination of pregnancy preferring a surgical termination of pregnancy [13, 15]. Where women have a preference for one method, typically  $\geq 90\%$  would choose the same method in the future [14, 16-18, 20]. Acceptability may be lower at later gestations; in the only randomised trial of abortion methods between 10-13 weeks, more women opted for VA again than medical abortion (79% vs. 70% respectively) [15]. However response rates were low (<50%). The results reported above are based on the 'single question with a binary outcome' approach to assessing acceptability. Such measures are simple to collect and report but provide limited information, particularly about why respondents hold the views they do. One supplementary approach is to ask respondents to rate specific features of their care thereby providing information about the reasons underlying acceptability judgements. Using a semantic differential rating scale, Henshaw et al. [14] identified that in randomised women, medical abortion rated lower on 6 of the bipolar adjectives with pain showing by far the largest difference. Vacuum aspiration was also rated less painful in women allocated according to preference.

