# **13 RANDOMISATION**

Participants with a procedure preference will decide whether to opt for a medical or surgical termination.

Participants with no preference, and willing to be allocated a procedure at random, will be randomised using a computer system with web-based access for trial personnel (PowerTrial). Randomisation will be stratified according to gestation (less than 9 weeks and between 9 & 13 weeks) and for previous termination of pregnancy.

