# **15.2 Sample size calculation**

The power of the study is based on the main comparison of acceptability between women randomised to medical or surgical TOP. Assuming the acceptability of medical termination to be 75%, we would need responses from 335 women in each randomised arm to detect a difference in acceptability of 10% (i.e. from 75% to 85%) with a significance level of 5% and power of 90%. We believe this difference in the level of acceptability is important for both consumers and providers; a similar difference was employed by Ashok et al [15] in their large randomised comparison of abortion methods.

Based on the power calculation we need primary outcome data on 670 women randomised to medical or surgical TOP at <14 weeks' gestation. In order to achieve this number we calculated;

- 1. 1116 women need to be randomised (assuming 40% of women randomised fail to attend for follow up and primary outcome data is therefore not available).
- 2. 2232 women need to be recruited (assuming 50% of women agreeing to participate in the study have a preference for medical or surgical TOP and are therefore not suitable for randomisation).
- 3. 3188 women need to be approached (assuming 30% of women accepted for TOP will decline involvement in the study).

Justification for assumptions – All three assumptions were based on our experience from an earlier pilot trial conducted at the RVI involving women requesting TOP at 9-13 weeks' gestation. For reasons detailed in [25] we believe our assumption of 60% follow up is conservative. Further, previous trials conducted in the UK have reported that 54% [14] and 82% [15] of recruited women undergoing TOP at < 9 weeks and 9-13 weeks respectively were prepared to have their method of TOP determined by randomisation. Thus our estimate of 50%

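### The tertiary aim (does receiving a preferred method improve outcomes?) cannot be answered by this design, and the pooled comparisons do not name the terms that would guard against an uneven choice of method

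*Protocol*

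**What the plan says.** Section 15.1 defines four groups: randomised medical (RM), randomised surgical (RS), preference medical (PM) and preference surgical (PS). The main comparison is RM against RS.

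The next tier is headed "Secondary comparison of medical and surgical arms (preference and randomised subgroups combined"), that is, RM+PM against RS+PS. Acceptability, quality of care, psychological and rating scales, emergency admission and symptoms are to be adjusted for key baseline variables, which are not listed. The last item, willingness to pay (WTP) in the combined groups, states no adjustment.

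The third tier sets preference women against randomised women on acceptability and on the psychological and rating scales, using the same methods as the second tier. Its purpose is stated as: "The aim of this comparison is to determine if receiving a preferred intervention improves key outcomes".

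Section 13 says who is randomised: "Participants with no preference, and willing to be allocated a procedure at random". Section 15.1 also expects every woman to get her randomised or preferred procedure. The table of events in Section 9 records strength of preference before the procedure in the preference group only.

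**The concern.** There are two problems, of different weight.

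The first is the question itself. To learn whether receiving a preferred method helps, one needs women with a preference who received it and comparable women with a preference who did not. The protocol plans no one in the second category.

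The second is the mix of methods. Randomisation should make the medical-to-surgical ratio about 1:1 among randomised women, but preference women choose for themselves. Unless they split evenly, method and preference status are correlated across the four groups. A pooled method comparison without a term for preference status then credits part of any preference-status difference to the more popular method. A preference-against-randomised comparison without a term for method credits part of any method difference to preference.

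At stake are the conclusions drawn from the second and third tiers. A reader could be told that one method is more acceptable, or that getting one's choice improves outcomes, when the data show neither.

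**Working it through.** **Can the tertiary aim be answered?** Setting Sections 9, 13 and 15.1 side by side:

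| Type of woman | Present in the design? |
|---|---|
| Has a preference, receives it | Yes: PM, PS |
| Has a preference, does not receive it | No group planned |
| Has no preference | Yes: RM, RS |

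The aim contrasts the first two rows; the planned comparison contrasts the first and third. Baseline adjustment cannot supply the missing row, because having a preference is what defines the groups. No pre-procedure strength of preference is recorded for randomised women, so graded preference cannot be used instead. The acceptability question in Section 14.1 (same method again?) also asks preference women about a choice they have already made once.

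**The plan's own sample size.** Section 15.2 says "we would need responses from 335 women in each randomised arm", for 75% against 85%, "with a significance level of 5% and power of 90"%. With a two-sided test and pooled variance under the null:

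n = [1.96 × √(2 × 0.80 × 0.20) + 1.2816 × √(0.75 × 0.25 + 0.85 × 0.15)]² / 0.10² = (1.1087 + 0.7193)² / 0.01 = 334.2, so 335 per arm.

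This reproduces and is not in dispute.

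**Inputs for the mix calculation**

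- Randomised responders: 670 (335 per arm), Section 15.2.
- Preference responders: half of 2232 is 1116; at 60% follow-up, 1116 × 0.60 = 669.6, taken as 670. The protocol states 60% for randomised women; applying it to preference women is an assumption.
- Acceptability by method: 75% and 85%, Section 15.2.
- Acceptability among preference women: Section 7 reports, "Where women have a preference for one method, typically" at least 90% would choose the same method again. I use 90%.
- Acceptability among randomised women under no method effect: 80%, the midpoint of 75% and 85% (assumption).
- Share s of preference women choosing surgery: not given. Section 7 says only that preference for surgery appears to rise with gestation. I vary s from 20% to 90%.

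All rates below are for crude two-proportion comparisons, normal approximation, two-sided 5%.

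**Pooled method comparison, no method effect in either stratum.** With 80% in RM and RS and 90% in PM and PS:

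- Medical: (335 × 0.80 + 670(1 − s) × 0.90) / (335 + 670(1 − s))
- Surgical: (335 × 0.80 + 670s × 0.90) / (335 + 670s)

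At s = 80%: medical (268 + 120.6) / 469 = 82.9%; surgical (268 + 482.4) / 871 = 86.2%; difference 3.3 points. The overall proportion is 85%, so SE = √(0.85 × 0.15 × (1/469 + 1/871)) = 2.05 points. The ratio is 1.61, and the chance of a significant result is Φ(1.61 − 1.96), about 36%.

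**Tertiary comparison, no preference effect.** With 75% medical and 85% surgical in both strata, randomised women average 80% and preference women 75 + 10s, so the spurious difference is 10 × (s − 0.5) points. At s = 80% this is 83% against 80%; SE = √(0.815 × 0.185 × 2/670) = 2.12 points; rejection about 29%.

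| s | Pooled: spurious difference (points) | False-positive rate | Tertiary: spurious difference (points) | False-positive rate |
|---|---|---|---|---|
| 20% | -3.3 | 36% | -3.0 | 27% |
| 50% | 0 | 5% | 0 | 5% |
| 70% | 2.1 | 18% | 2.0 | 15% |
| 80% | 3.3 | 36% | 3.0 | 29% |
| 90% | 4.8 | 61% | 4.0 | 48% |

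The two halves of the table are separate illustrations with different assumptions about preference women. They are not a joint forecast.

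**Effect of the extra terms.** In these null scenarios, stratifying the pooled comparison by preference status, or the tertiary by method, brings the expected difference to 0 at every s. With 75%/85% in randomised women and 90%/90% in preference women, the crude pooled difference is 2.2 points at s = 20% and 8.8 at s = 80%; the Mantel-Haenszel stratified difference is 6.1 at both. At s = 50% both methods give 5.0.

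**The case against.** The strongest reply is that the protocol does not exclude these terms. Most pooled comparisons are to be adjusted for baseline variables that are not listed. Preference status is known at baseline and could be among them, and a covariate list commonly sits in a statistical analysis plan, which is not at hand. A reader might infer that the protocol omits preference status and method; the text supports only that it does not name them. The reply is weaker in two places. Method received is not plainly a baseline variable, so the tertiary reference to the secondary methods does not clearly cover it. And the pooled WTP item mentions no adjustment at all.

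A reader might also take both comparisons as certain to be confounded, or the false-positive rates as forecasts. The documents support neither. The split is not given; the artefact vanishes at 50:50 and reverses below it. The pooled artefact also needs preference status to affect the outcome, and the tertiary one needs a method effect. Section 7 gives 63-92% acceptability in randomised trials before 9 weeks, which overlaps the figure of at least 90% for preference women. The rates are for crude tests, whereas the protocol plans adjusted regression for acceptability. All of this stands and limits the second problem to a conditional one.

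None of it rescues the tertiary aim. Section 15.1 does plan a four-group baseline comparison, but for the purpose of extrapolating the randomised result. No choice of covariates can create the missing group.

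**Conclusion.** The tertiary aim is wrong as written: the design compares having and receiving a preference with having none, not a met with an unmet preference. This follows from Sections 9, 13 and 15.1 and rests on no numerical assumption.

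The mix problem is a real but conditional weakness. Its size depends on the unstated share choosing surgery: under the stated assumptions it is nil at an even split and about 3 points in either direction when the split is 80:20 or 20:80. Naming the terms is a near-free safeguard.

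The main comparison of RM with RS, and its 335 responders per arm, are unaffected.

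**What to change.** 1. Restate the tertiary aim as a non-causal comparison of outcomes in women who have and receive a preference with those in women who have none.
2. Fit the pooled analyses, including WTP, with method, preference status and their interaction, plus the baseline covariates. Include method in the tertiary model.
3. Report method effects separately in randomised and in preference women. Give a combined estimate only from that model, and say that PM against PS remains self-selected: a preference-status term removes the mix artefact, not the selection.
4. If the statistical analysis plan already contains these terms, align the protocol wording with it.

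The cost is a few sentences and model terms, with no new data or participants. The tertiary claim becomes more modest, and the pooled estimate loses some precision.
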